Descriptive analyses will be conducted to characterize high risk PCa census tracts compared to lower risk census tracts. Mapping the high risk census tracts will help us to determine how they are distributed within and around pre-defined Philadelphia neighborhoods (commonly used community names for each section of the city, Figure 2.) Those Philadelphia neighborhoods will become the target

neighborhoods for aims 2 and 3. Continuous variables will be analyzed with t-tests (or nonparametric alternative tests for variables without normal distributions) and categorical variables will be analyzed with frequency tables and chi square tests or Fisher's exact tests if any expected cell frequencies are small. Patient-level and neighborhood variables will be summarized for comparisons between high risk and lower risk neighborhoods to highlight factors that may be central topics of focus groups and intervention development. Correlations will be computed to examine the relationship between percent of cases with advanced disease and prostate-specific mortality rates. Regression modeling will allow us to determine significant trends in PCa incidence and mortality over time with and without adjustment for covariates such as the prevalence of risk factors including older age at diagnosis, African American residents and low neighborhood SES. We will also use the EpiQMS tool provided on the PA Department of Health website to determine age-specific incidence and mortality rates for Philadelphia. Generating maps of these data along with maps showing highest prevalence of PCa screening (CHDB data) will indicate where should target our focus groups and interventions for aims 2 and 3.

B2.f. Designation of Neighborhoods for Study Condition

Based on the GIS mapping results, the four neighborhoods in Philadelphia with the highest rates of late-stage PCa will be chosen to serve as study sites. Study condition (intervention or control) will be designated at the neighborhood level. Therefore, two of the sites will be designated as intervention neighborhoods and two will be designated as control neighborhoods. All men who live in the same neighborhood will receive the same intervention. All efforts will be made to ensure that the designations are done in a way that Intervention and Control neighborhoods are not geographically adjacent to each other, to avoid contamination of study messages among participants.

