Men from both groups who decide that they want to be screened for prostate cancer will be linked with medical care at Thomas Jefferson University Hospital (TJUH) if the participant does not have a primary care physician for medical care. Participants will be encouraged to contact their primary care physician for screening, or in the absence of a primary care physician, [name] at TJUH, a study co-investigator and oncologist who specializes in high-risk populations, will provide screening at TJUH. In addition, [name] will care for any male who completes screening and requires follow-up medical care based on his test results. A letter of support

from [name] attesting her commitment to provide thorough medical care for any male who screens for prostate cancer as a result of this project is included in the application.

B.4.d. Analysis Plan

Since Aim 3 will not be addressed by a randomized trial design and we anticipate clustering of observations from the same neighborhood, linear and generalized linear mixed models having random intercepts corresponding to neighborhood will be applied to test the quantitative hypotheses. This approach will allow us to account for the correlation between participants from the same neighborhood and adjust the parameters of interest for potential confounding variables. Potential confounders will be identified and choices about specific models will be made after computing descriptive statistics to compare the distributions and identify imbalances of study variables between the groups (i.e., intervention vs. control) or variables (e.g., the number of barriers to screening) of interest for the given hypothesis. If substantial clustering also exists at the site level, this hierarchical correlation will also be incorporated into the models.

A sub-aim of this study will be to determine whether there are differences in results based on where the intervention is implemented. As neighborhoods often attract certain demographics of the population, so do various gathering places for men. Some gathering places may prove to be better for achieving the goals of this study – increasing PCa knowledge and shared decision making about PC a screening among high risk men. During aim 2, the content will be optimized for each setting and suggestions will be made for future interventions in these settings.

B.4.e. Power Analysis

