The target sample size is $n=200$ men. Since we anticipate 20% attrition, we will recruit and consent 240 evenly distributed across each of the 4 neighborhoods. In a local population similar to our target population, a previous prostate cancer screening decision making study [21] found that, compared to standard intervention controls, their decision support enhanced intervention lead to a 0.8 point increase ($SD = 1.5$) in knowledge on a 10-point scale. Assuming this in our target population, a type I error rate of 0.05, an intra-neighborhood correlation of 0.005 to 0.01, and that 4 to 10 neighborhoods will be sampled per group, the planned study should have approximately 80% to 94% power to detect this difference. In a similar prostate cancer screening shared decision making article [22], investigators found that their intervention lead to a 22% reduction ($SD = 0.15$) in prostate screening. Making similar assumptions as for the knowledge endpoint, we may be somewhat underpowered for detecting this difference in screening rates as the expected power would be approximately 50% to 67%. However, the primary goal is to increase knowledge about screening so that each man will make an informed decision taking into account his risk factors and personal preferences.

B.4.f. Results Dissemination

The study results will be disseminated to the neighborhood at the end of the project by multiple methods. Town hall meetings will be held in the targeted neighborhoods to explain the goals of the study and to provide a summary of results and additional PCa education to the community at-large. Next steps will be discussed, as well as ways to improve, sustain and expand targeted educational interventions around the Philadelphia region. Project newsletters and brochures will be made available to be shared with family and community members. The video developed during aim 2 for educational purposes will be shared at the town halls and will be made available on the internet for public education.

C. Potential Problems and Alternative Approaches

C.1. Geocoding

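### With two neighborhoods per condition the intervention test has 2 degrees of freedom, and the planned random-intercept model, with no small-sample method named, does not hold 5% error with a z or a 2-df t reference

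*Combined protocol and SAP*

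**What the plan says.** Section B2.f fixes the unit of assignment: "Study condition (intervention or control) will be designated at the neighborhood level". It adds that "two of the sites will be designated as intervention neighborhoods and two will be designated as control neighborhoods", and that "All men who live in the same neighborhood will receive the same intervention".

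Section B.4.d gives the analysis: "linear and generalized linear mixed models having random intercepts corresponding to neighborhood will be applied to test the quantitative hypotheses". It presents this as the way to account for correlation within neighborhoods and to adjust for confounders. Sites are handled conditionally: "If substantial clustering also exists at the site level, this hierarchical correlation will also be incorporated into the models".

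Section B.2.d sets significance at p < 0.05 and names the software. Neither section states an estimator (REML or ML), a reference distribution, a denominator df or a small-sample correction.

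Section B.4.e assumes that "4 to 10 neighborhoods will be sampled per group" with "an intra-neighborhood correlation of 0.005 to 0.01", for an intervention that "lead to a 0.8 point increase ($SD = 1.5$) in knowledge on a 10-point scale". It reports about 80% to 94% power. The same section spreads recruitment evenly over 4 neighborhoods in total.

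**The concern.** Every man in a neighborhood gets the same condition, so the intervention effect is a comparison of two neighborhood means with two others. The information on how much neighborhoods differ for other reasons comes from 2 df, however many men are enrolled. With so few clusters the reference distribution largely decides the result: the two-sided 5% critical value is 4.303 on 2 df and 1.960 for z.

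A second difficulty is specific to the random-intercept model. At small ICCs the fitted neighborhood variance is often exactly zero, and the model then behaves as if the men were independent. A z test is too liberal in those samples. Putting a 2-df t on the truncated variance swings far the other way. Hypotheses 3a and 3c would be judged by a test whose error rate is not 5% and depends on an unstated option.

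Leaving site in or out of the model according to whether its clustering looks substantial adds another choice made on the data.

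**Working it through.** **Inputs.** Two neighborhoods per condition (B2.f). n = 200, SD 1.5, difference 0.8, ICC 0.005 to 0.01, α = 0.05 (B.4.e); two-sided testing is assumed. With 4 neighborhoods, m = 200/4 = 50 men each.

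**1. The plan's own power figure.** With k neighborhoods per group, m = 200/(2k), DE = 1 + (m − 1)·ICC, SE = 1.5·√(2·DE/100), and noncentral t on 2(k − 1) df:

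- k = 4, ICC 0.01: DE = 1 + 24 × 0.01 = 1.24; SE = 0.236; 0.8/0.236 = 3.39; 6 df; power 80.4%.
- k = 10, ICC 0.005: DE = 1 + 9 × 0.005 = 1.045; SE = 0.217; 0.8/0.217 = 3.69; 18 df; power 93.7%.

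This matches 80% to 94%. A normal reference gives 92.3% and 95.8%, which misses the lower end. The stated power is therefore consistent with between-neighborhood df, but with 6 to 18 of them.

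**2. The same formula at the design's k = 2 (2 df).**

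| ICC | DE | SE | 0.8/SE | Power, 2 df | 4.303 × SE | 1.960 × SE |
|---|---|---|---|---|---|---|
| 0.005 | 1.245 | 0.237 | 3.38 | 45.6% | 1.02 | 0.46 |
| 0.01 | 1.49 | 0.259 | 3.09 | 40.3% | 1.11 | 0.51 |

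With 240 × 0.8 = 192 men analysed, power is 44.6% and 39.6%.

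The half-widths in the table use the true SE. The SE estimated on 2 df averages √π/2 = 0.886 of the true one, so the average reported 2-df half-width is 0.90 to 0.99. For REML with z the simulated average is about 0.50 to 0.53.

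**3. Type I error of the random-intercept model.** The simulation is balanced, linear and unadjusted, with total variance 1 and λ = 1 + 49·ICC:

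- difference ~ N(0, 2λ/100)
- between-neighborhood mean square MSB ~ λ·χ²₂/2
- within-neighborhood mean square MSW ~ (1 − ICC)·χ²₁₉₆/196
- REML uses MSB if MSB > MSW, and otherwise the pooled mean square.

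| ICC | Variance estimated as zero | REML, z | REML truncated, 2-df t | Neighborhood means, 2-df t |
|---|---|---|---|---|
| 0 | 63% | 3.8% | under 0.01% | 5.0% |
| 0.005 | 55% | 5.6% | 0.01% | 5.0% |
| 0.01 | 48% | 7.1% | 0.03% | 5.0% |
| 0.05 (assumed) | 24% | 13.8% | 0.8% | 5.0% |
| 0.10 (assumed) | 14% | 16.4% | 2.0% | 5.0% |

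The zero-estimate column agrees with the approximation 1 − exp(−(1 − ICC)/λ): 1 − exp(−0.995/1.245) = 0.55 and 1 − exp(−0.99/1.49) = 0.49. Residual df (196) in place of z gives 5.4% to 7.0% at the planned ICCs. ML with z gives 7.3% to 9.7%.

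**4. How to adjust.** B.4.d expects imbalance between groups. Suppose slopes are fitted without condition and the residuals are then compared. One covariate differing by d within-group SDs between equal groups shrinks a true effect τ to τ/(1 + d²/4). For τ = 0.8 this is 0.8/1.0625 = 0.75 at d = 0.5 and 0.8/1.25 = 0.64 at d = 1.0 (both d values assumed). Slopes fitted with condition in the model avoid this.

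**The case against.** A reader might infer that the plan's p-values and intervals will be too favourable. The documents do not support that as fact. B.4.d names neither a z test nor residual df, nor REML or ML; a 2-df reference is unspecified, not excluded. At the plan's own ICCs the excess under REML with z is modest, and at ICC 0 that test is conservative. Error rates of 14% to 16% need ICCs that appear nowhere in the documents, and nothing in them shows the planned ICC to be optimistic. All of this stands.

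A reader might also infer that the analysis and power sections disagree about df. They cannot, because the analysis section is silent; the power reconstruction even suggests that cluster-level df were in mind. The real conflict is the number of neighborhoods: 2 per group in B2.f and 4 to 10 in B.4.e.

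On sites, B.4.d does not say that a significance test decides what is substantial, and for the condition contrast a neighborhood-level test absorbs site clustering anyway. That part is secondary.

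The objection does not remove the point. Stating a 2-df reference would not rescue the planned model, because a 2-df t on a variance truncated at zero gives about 0.01% to 0.03% error. The model is off target with either reference.

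**Conclusion.** The concern holds in this form. The condition effect has 2 df, no small-sample method is specified, and at ICC 0.005 to 0.01 the random-intercept model gives about 5.6% to 7.1% type I error with z or about 0.01% to 0.03% with a 2-df t on the truncated variance. A 2-df t test on neighborhood means holds 5.0%. On the design as written, power for 0.8 points is about 46% to 40%, not 80% to 94%.

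This rests on a balanced, unadjusted, linear model with normal errors, two-sided testing and 50 men per neighborhood. Hypothesis 3c was not simulated separately because its scale is not defined, and neither was a generalized model for screening. The 2-df structure applies to both; the exact error rates may not. Confounding from non-randomised neighborhoods is a separate issue that no choice of df resolves.

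**What to change.** In B.4.d, before outcome data are seen, make the main test of the condition effect a neighborhood-level comparison:

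1. Estimate covariate slopes, including the baseline score, from an individual-level model that contains condition or neighborhood fixed effects.
2. Form the four adjusted neighborhood means.
3. Compare the two conditions with a t test and 95% interval on 2 df (critical value 4.303), leaving the between-neighborhood variance untruncated.
4. Report the mixed model as supportive, with its estimator and df method stated.

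This also absorbs site and session clustering for the condition contrast, so that result no longer depends on whether site clustering is judged substantial. Because the slopes are themselves estimated, the 2-df reference is approximate when imbalance is large; say so.

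In B.4.e, reconcile the number of neighborhoods per group with B2.f and restate power. With two per group it is about 46% (ICC 0.005) to 40% (ICC 0.01).

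The cost is analysis text and some programming, wider intervals (half-width roughly 0.9 to 1.1 points at SD 1.5, against an assumed effect of 0.8), and an open statement that the design as written has less than even power for its main hypothesis. Enrolling more men in the same four neighborhoods would not add df; only more neighborhoods would.

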Informed Consent and Baseline Survey: The health educator will obtain informed consent from each participant by reviewing the consent document and answering any questions about the study. After signing the consent document, participants will complete a brief pencil-and-paper baseline questionnaire. Items to be assessed at baseline include knowledge about prostate cancer and screening, attitudes towards screening, subjective norms about screening, decisional conflict about screening, and intentions to screen. Knowledge about prostate cancer and screening will be measured with a 17-item scale, recently validated with a sample of African American males. [18] The measure for decisional conflict will be constructed from O'Connor's Decisional Conflict Scale, a frequently used assessment for anxiety about decision making.[19] This scale includes a self-efficacy subscale that pertains to whether the participant feels 'a lot confident', 'a little confident', or 'not at all confident' about making an informed health decision. Demographic data related to age, race/ethnicity, family history of prostate or other cancer, and other pertinent health information will be collected. Additionally, contact information (telephone number(s), email address, and mailing address) for each participant will be collected to aid in maintaining communication with enrolled participants for post-survey completion.

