Study Intervention: Men who live in the Intervention Group Neighborhoods: After obtaining informed consent and administering the baseline survey, the health educator will show the short introductory video on a tablet computer. Then, the educator will use the curriculum booklet, one given to each participant, to review general information about the prostate gland, prostate incidence and development, risk factors, screening options, screening guidelines and the importance of repeat screening.[20] The educational session is meant to be interactive, with men feeling comfortable to ask questions and engage in a discussion with the educator and the other men at the session. Men Who Live in the Control Group Neighborhoods: After obtaining informed consent and administering the baseline survey, the health educator will show the short introductory video on a tablet computer. Then, the educator will use the curriculum booklet, one given to each participant, to review topics about health promotion actions related to diet, exercise, tobacco, general cancer screening and cardiovascular risk. The educational session is meant to be interactive, with men feeling comfortable to ask questions and engage in a discussion with the educator and the other men at the session. It is anticipated that the educational sessions for both groups will last about 15 minutes.

Post-Survey(s): Immediately following the intervention, men will complete a brief paper-and-pencil endpoint survey. The majority of items on the baseline survey, except for the demographic and contact information, will be repeated on the endpoint survey. Additionally, the study research assistant will call each enrolled participant at 1 month and 4 months after their enrollment date to administer the same endpoint survey. Participants who are not reached by telephone will be contacted by mail and by email to attempt to retain the maximum number of participants over time.

Participant Compensation: Participants will be compensated \$25.00 after completing the endpoint survey on the day of the intervention and \$25.00 for the completion of each follow-up survey.

Referral to Screening

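### The Aim 3 model does not commit to each man's baseline score and picks covariates from observed group imbalances, so some baseline confounding can remain and precision may be lost

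*Combined protocol and SAP*

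**What the plan says.** Section B.4.d acknowledges that allocation is not random: "Since Aim 3 will not be addressed by a randomized trial design and we anticipate clustering of observations from the same neighborhood". The model is given as "linear and generalized linear mixed models having random intercepts corresponding to neighborhood will be applied to test the quantitative hypotheses", with a site level to be added if clustering there is substantial. Adjustment for confounders is intended, but its content is left open: "Potential confounders will be identified and choices about specific models will be made after computing descriptive statistics", the purpose of those statistics being "to compare the distributions and identify imbalances of study variables between the groups (i.e., intervention vs. control" or across another variable of interest. The section gives no covariate list, no rule for what counts as an imbalance, no baseline-outcome term and no time point for the analysis.

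Section B.4.c describes the data available before the session: "Items to be assessed at baseline include knowledge about prostate cancer and screening, attitudes towards screening, subjective norms about screening, decisional conflict about screening". The baseline questionnaire also covers screening intentions, age, race/ethnicity and family history. After the session, "The majority of items on the baseline survey, except for the demographic and contact information, will be repeated on the endpoint survey". The same endpoint survey is given by telephone at 1 and 4 months.

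Section B.4.e sets the scale: "The target sample size is $n=200$ men", a 0.8-point knowledge difference with SD 1.5, and ICC 0.005 to 0.01. Section B2.f assigns two neighborhoods to each condition.

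**The concern.** The study collects pre and post scores, but the analysis does not say that the pre score will be used. In a randomized trial that would mainly cost precision. Here whole neighborhoods are designated to a condition, so differences in starting knowledge are to be expected and carry directly into the comparison of post-session scores.

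Screening covariates for imbalance is a weaker safeguard than naming them. It depends on the sample gap that happens to be seen and ignores how strongly the covariate predicts the outcome. It also means that the model for the main result is chosen with group differences in view. Knowledge is the endpoint that section B.4.e calls the primary goal, so this affects the central result.

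**Working it through.** **Inputs from the documents.** 200 men, 100 per group; effect 0.8; SD 1.5; type I error 0.05 (taken as two-sided); ICC 0.005 to 0.01; 4 to 10 neighborhoods per group in the power section, 2 per group in the design.

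**Assumptions, not in the documents.** Baseline-to-follow-up correlation r of 0.3 to 0.7; for the bias check, a true baseline gap of 0.2 SD, slope 0.6 and equal SDs of 1.5 before and after; several possible imbalance triggers.

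**Step 1: reproduce the stated power.** With k neighborhoods per group, m = 100/k, design effect DE = 1 + (m − 1) × ICC, SE = 1.5 × √(2 × DE/100), and a noncentral t with 2(k − 1) df.
- k = 4, ICC 0.01: DE = 1 + 24 × 0.01 = 1.24; SE = 0.236; 0.8/SE = 3.39; 6 df; power 80.4%.
- k = 10, ICC 0.005: DE = 1 + 9 × 0.005 = 1.045; SE = 0.217; 0.8/SE = 3.69; 18 df; power 93.7%.

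This matches the stated 80% to 94%, with no further reduction of the SD of 1.5 for baseline.

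**Step 2: the design as planned.** k = 2, ICC 0.01: DE = 1 + 49 × 0.01 = 1.49; SE = 0.259; 0.8/SE = 3.09; 2 df; power 40.3%.

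**Step 3: precision from baseline adjustment.** If 1.5 is a raw-score SD, adjustment multiplies the variance by 1 − r². This assumes that baseline explains variance between and within neighborhoods equally.

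| r | 1 − r² | SE | Power (k = 2, ICC 0.01) |
|---|---|---|---|
| not adjusted | 1.00 | 0.259 | 40% |
| 0.3 | 0.91 | 0.247 | 43% |
| 0.5 | 0.75 | 0.224 | 49% |
| 0.7 | 0.51 | 0.185 | 62% |

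If 1.5 is a change-score SD, the 40% belongs to a change-score analysis. The variance factor for adjusting is then (1 − r²)/(2(1 − r)) = (1 + r)/2. At r = 0.5 this is 0.75, SE 0.224, power 49%; at r = 0.7 it is 0.85, SE 0.239, power 45%.

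**Step 4: confounding left by imbalance screening.** If baseline is never adjusted, bias = 0.6 × 0.2 × 1.5 = 0.18 points, and 0.18/0.8 = 22.5% of the planned effect. When adjustment happens only if a trigger is met, simulation at individual level (100 per group, no clustering) gives:

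| Rule | Gap flagged | Mean bias (points) | Share of 0.8 |
|---|---|---|---|
| never adjust | 0% | 0.18 | 22.5% |
| adjust if p < 0.05 | 29% | 0.08 | 10% |
| adjust if p < 0.20 | 56% | 0.03 | 4% |
| adjust if standardized difference > 0.1 | about 78% | 0.006 | under 1% |
| always adjust | n/a | 0 | 0% |

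The result depends heavily on the trigger, and the plan names none.

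**The case against.** The plan promises to adjust for confounders, and baseline knowledge is a study variable that the imbalance check would naturally cover. Leaving the model choice open does not rule out covariance analysis or change scores. Looking for imbalance is an ordinary step in a non-randomized comparison, and under a sensitive trigger the residual bias nearly vanishes. All of this stands. The defect is a missing commitment, and the plan does not exclude the baseline score.

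The precision figures rest on a correlation that the documents do not give and on an SD whose type is not stated. That also stands, which is why both readings are shown. Most of the fall from the stated 80% to 94% down to 40% comes from having two neighborhoods per group, which is a separate matter.

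Two stronger readings are tempting. The first is that the plan carries a 0.18-point bias, 22.5% of the effect. That figure describes an analysis that never adjusts for baseline, and the plan does not say that. The second is that the three post-session surveys will be treated as independent, since the only stated random effects are for neighborhood and possibly site. If they were pooled in that way with within-man correlation 0.5 to 0.7, individual-level standard errors would be too small by √(1 + 2r) = 1.41 to 1.55, and type I error would be 17% to 21%. No section says that the surveys will be pooled, so this is a hazard to close off. It is not an error in the plan.

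**Conclusion.** The point holds as a gap in pre-specification with a free remedy. Always including the baseline score is better than including it only when it looks imbalanced. Under the stated assumptions, the imbalance rule leaves a mean bias between about 0.006 points (standardized-difference trigger 0.1) and 0.08 points (p < 0.05 trigger) on a planned 0.8.

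Where baseline is left out, power at 2 neighborhoods per group and ICC 0.01 is 40%, against 43% to 62% with it, for r from 0.3 to 0.7 and a raw-score SD. Under the change-score reading, adjustment gives 49% to 45% for r from 0.5 to 0.7.

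The argument reaches H3a and H3c, and H3c only where its scale is among the repeated items. H3b relates barriers to anxiety and is not a comparison of conditions. Baseline adjustment does not remove differences between neighborhoods that are aliased with condition, and it does not bring power back to the stated range.

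**What to change.** Rewrite the Aim 3 model text in section B.4.d before data are examined:

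- For H3a and H3c, state the primary model as post-session score on condition and the same scale's baseline score, always included where the scale is repeated, with the neighborhood random intercept.
- Add a short named list of individual covariates already collected, for example age, race/ethnicity and family history. Keep covariates chosen on observed imbalance for sensitivity analyses.
- Name the post-session survey that is primary. If more than one enters a model, include time, condition-by-time and a participant random effect.
- In any model of screening uptake, adjust for baseline intention.
- State whether SD 1.5 is a raw-score or change-score SD, and acknowledge that neighborhood-level confounding remains.

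The cost is about one paragraph of analysis text. No new data, visits or participants are needed.

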(2) To develop, using a mixed methods approach, a targeted educational intervention about prostate cancer for men who live in high risk neighborhoods

No hypothesis is being tested for this aim.

(3) To test the impact of the targeted intervention on levels of knowledge, anxiety, and informed decision making about PCa screening

Hypothesis 3a: Men in the prostate-specific intervention group will have higher levels of knowledge about PCa screening than those who receive the healthy lifestyle control intervention

Hypothesis 3b: Men who express a greater number of barriers to PCa screening will have higher levels of anxiety about PCa and PCa screening

Hypothesis 3c: Men in the prostate-specific intervention group will have higher levels of informed decision making about PCa screening than those who receive the healthy lifestyle control intervention

Sub-aim: To examine if there are differences in outcomes by intervention setting

(4) To observe the rates of PCa screening in the intervention and control groups

B. RESEARCH STRATEGY

B.1. Experimental Design

The proposed design is a mixed-methods study including quantitative analyses of state registry data, survey data and Philadelphia health statistics, qualitative analyses of focus group results, and the test of a targeted intervention to improve key factors associated with shared decision making and potential uptake of prostate cancer screening in high-risk neighborhoods. Table 2 provides a brief summary of the study populations, study outcomes, traits to be measured, and analytical methods proposed to accomplish each specific aim.

Table 2: Summary of Specific Aims and Study Methods

	Aim 1: Identify high risk neighborhoods	Aim 2: Develop intervention via mixed-methods approach	Aim 3: Test intervention in high risk neighborhoods
Sample Population	Estimates from 1995-2005 data: ~4,500 African-Amer. cases ~4,000 European Amer. Cases		200 At-Risk Men
Primary Outcomes	Prostate cancer mortality; tumor stage and grade		Prostate cancer knowledge, anxiety, intention to screen, PSA screening
Neighborhood Data	Demographics, PCa screening, other health behaviors, health conditions, SES		
Patient-Level Data	Race, age, marital status	Focus Group Results	

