It is anticipated that the small-group educational sessions will occur at sites that frequently draw middle-aged and senior men from the target population in each pre-selected neighborhood. This will include churches, barbershops, recreational centers, community development corporations, employment centers, and neighborhood restaurants. [54] MEE will identify and engage these types of establishments in each target neighborhood by drawing upon its vast network of community partners in Philadelphia. MEE will also conduct phone book and Internet searches to identify potential recruiting locations and sites for educational sessions. They will introduce the study to the leadership of each location and explain the requirements of holding a study intervention session at their facility. MEE will create informational packets for interested study sites to aide in the discussion. The only requirement of a study site is to provide a space for which the research team can conduct a study session. Recruitment for the study session will be done by the study team, although a site is welcome and encouraged to invite eligible men who it has contact with. Sites may agree to hold more than one session, provided that the study team leadership feels that an adequate number of participants can be recruited at that site. Study sites will be compensated based on the number of study sessions that occur on their premises.

B.4. Aim 3: To test the impact of the targeted intervention on levels of knowledge, anxiety, and informed decision making about PCa screening

B.4.a. Participant Recruitment

MEE will develop an e-mail blast, flyers for study site partners and recruiting information to recruit eligible men from the neighborhoods for participation. If these efforts need to be augmented, MEE will also conduct canvassing of key transportation corridors in the selected Philadelphia neighborhoods, to recruit potential study participants. The study team will also draw upon the community contacts and resources of the Penn Center for Community Health Workers to identify men eligible for participation. The goal is to enroll 200 men in the study over a period of 18 months. We anticipate, based on our previous experience in community-based research, that we will have to screen about 10 times that number, or about 2000 men, to reach our study recruitment goals.

B.4.b. Study Eligibility

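### Consenting 240 men with 20% attrition leaves about 192, not the target of 200, and B.4.a gives a different enrollment number (200) from B.4.e (240)

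*Combined protocol and SAP*

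**What the plan says.** B.4.e (Power Analysis) opens with the target: "The target sample size is $n=200$ men". It continues: "Since we anticipate 20% attrition, we will recruit and consent 240 evenly distributed across each of the 4 neighborhoods". The power for knowledge is built on "a 0.8 point increase ($SD = 1.5$) in knowledge on a 10-point scale", with "a type I error rate of 0.05, an intra-neighborhood correlation of 0.005 to 0.01, and that 4 to 10 neighborhoods will be sampled per group", and is given as approximately 80% to 94%.

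B.4.a (Participant Recruitment) gives a different number at the point of entry: "The goal is to enroll 200 men in the study over a period of 18 months". The screening load follows from it: "we will have to screen about 10 times that number, or about 2000 men, to reach our study recruitment goals".

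Table 2 in B.1 lists the Aim 3 sample as "200 At-Risk Men", without saying whether this is before or after losses. B.4.c (Study Intervention) describes follow-up: "the study research assistant will call each enrolled participant at 1 month and 4 months after their enrollment date". No section reconciles 200 enrolled with 240 consented.

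**The concern.** There are two discrepancies. First, the allowance for attrition is added to the target rather than divided out, so the number consented does not yield the number the power statement uses. Second, the section that recruiting staff will work from stops at 200, while the section that justifies the sample size needs 240.

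The second matters more in practice. A recruitment target tells staff when to stop. A team following B.4.a would stop 40 men before a team following B.4.e, and its screening effort would have been planned for 200 entrants. At stake are the power for knowledge, which B.4.e names as the primary goal, and a clear definition of when recruitment is complete.

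**Working it through.** **Inputs.** From B.4.e: target 200, attrition 20%, consented 240, 4 neighborhoods, difference 0.8, SD 1.5, alpha 0.05, intra-neighborhood correlation (ICC) 0.005 to 0.01, 4 to 10 neighborhoods per group. From B.4.a: 200 enrolled, about 10 screened per man enrolled. The plan does not state whether the test is one- or two-sided; two-sided is assumed.

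**Step 1: the plan's 240.** 200 × (1 + 0.20) = 240 reproduces the stated figure exactly.

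**Step 2: what 240 delivers.** 240 × (1 − 0.20) = 192, or 48 per neighborhood, which is 8 men (4%) short of 200. The number needed to keep 200 is 200/(1 − 0.20) = 250. That is 62.5 per neighborhood, so equal whole numbers need 4 × 63 = 252. Consenting 240 would keep 200 only if attrition were 1 − 200/240 = 16.7%.

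**Step 3: B.4.a read literally.** 200 × 0.80 = 160, which is 40 men (20%) short.

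**Step 4: which number the power statement uses.** Let N be the men analysed and k the neighborhoods per group. Then:

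- men per neighborhood: m = N/(2k)
- design effect: DE = 1 + (m − 1) × ICC
- standard error: SE = 1.5 × √(2 × DE/(N/2))
- noncentrality: 0.8/SE, with power from a noncentral t on 2(k − 1) degrees of freedom

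At N = 200:

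- k = 4, ICC 0.01: m = 25, DE = 1.24, SE = 1.5 × √(2.48/100) = 0.236, noncentrality 3.39 on 6 df, power 80.4%.
- k = 10, ICC 0.005: m = 10, DE = 1.045, SE = 1.5 × √(2.09/100) = 0.217, noncentrality 3.69 on 18 df, power 93.7%.

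These match the stated 80% to 94%.

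**Step 5: the same calculation at other numbers analysed.**

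| Men analysed | k = 4, ICC 0.01 | k = 10, ICC 0.005 |
|---|---|---|
| 240 (no loss) | 85.5% | 96.7% |
| 200 (target) | 80.4% | 93.7% |
| 192 (240 less 20%) | 79.2% | 92.8% |
| 160 (200 less 20%) | 73.2% | 88.0% |

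The range at 240 does not match the stated one. So the knowledge power assumes 200 men after losses, not 200 or 240 at entry in a study that then loses some.

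**Step 6: screening load.** At the plan's own ratio, 10 × 240 = 2400 men, 400 more than the 2000 in B.4.a.

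**The case against.** The best defence is that the effect is small. At 192 the power for knowledge falls by about one point at each end of the range, and B.4.e describes its range as approximate. That stands: taken alone, the inflation error changes nothing of substance.

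Four stronger readings are tempting, and the documents do not support them.

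- **That the plan will end with 160 men.** B.4.e commits to consenting 240, and the goal in B.4.a may be a loose restatement of the net target. Table 2 repeats 200 without settling the matter. Against this, B.4.c calls men enrolled before their 1- and 4-month contacts, so the literal reading is a fair one. The 160 is therefore conditional on that reading.
- **That no analysis can reach 200 men.** The first endpoint survey is completed straight after a session of about 15 minutes, on the same day, with payment on completion. Few men should be lost by then. If nearly all 240 contributed, power under the plan's assumptions would be about 86% to 97%. The 20% bears mainly on the 1- and 4-month surveys, and the plan does not say which time point its 200 refers to. The mixed models in B.4.d might also use partial follow-up, but the text specifies only neighborhood intercepts, with hierarchical correlation at site level if needed, so this is only a possibility.
- **That attrition brings power below one half.** Power is that low only with the 2 neighborhoods per group that the design in B2.f provides, instead of the 4 to 10 assumed in B.4.e. By the same method it is already about 40% to 46% at a full 200 men. That gap is a separate and larger issue and is not counted here.
- **That every power figure rests on 200.** Only the knowledge range was reproduced. The 50% to 67% given for screening was not, so nothing is claimed about it.

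**Conclusion.** The figures in B.4.e do not agree with one another, and B.4.a conflicts with B.4.e on how many men enter the study. With 240 consented and the plan's own 20% loss, about 192 men remain, and power for knowledge is about 79% to 93% against the stated 80% to 94%. If B.4.a were followed literally, about 160 would remain, with power of about 73% to 88%.

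These results assume a two-sided 0.05 test, the plan's effect size, SD and ICC range, its assumed 4 to 10 neighborhoods per group, and a 20% loss at the time point analysed. The arithmetic is certain; the 160 depends on what enrolling means in B.4.a. The point is a minor correction, worth making because the recruitment target is an operational instruction and should have one value.

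**What to change.** Use one consent target, 240 men (60 per neighborhood), in both B.4.a and B.4.e. In B.4.e, state that about 192 men (48 per neighborhood) are expected after 20% attrition, name the survey time point this refers to, and restate power for 192. On the present assumptions that is about 79% to 93% for knowledge. The number of neighborhoods per group behind that range needs its own correction. In B.4.a, change the enrollment goal to 240 and the screening estimate to about 2400. In Table 2, say whether the sample shown is before or after attrition.

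Keeping 240 needs only wording changes to the sample size, but it makes explicit a screening effort about 400 men larger than B.4.a now plans. If the sponsor prefers to keep 200 after attrition, the consent target becomes 250, or 252 for equal neighborhoods. That is 10 to 12 more men, with about 2500 screened for 250.
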